10.6. Model building

10.6.1. General PKPD model building approach

Population models of the PK and PD will be developed in step-wise manner.

1. A population PK model will be developed to obtain individual PK parameter estimates based on which the individual PK profiles are described well.
2. A parasite growth model (parasite growth rate and deviation of parasitemia at inoculation from parasitemia at treatment administration) will be estimated from the total parasite counts before treatment administration. Estimation of typical and individual PD parameters will be performed with IQRtools SysFit. Other appropriate growth models, e.g. an oscillatory model, will be tested if advisable.
3. The PKPD model will be build using the individual PK parameter estimates and individual growth model parameter estimates as regression parameters. Estimation of typical and individual PD parameters will first be performed with IQRtools SysFit to investigate model identifiability and second with Monolix to additionally estimate IIV.

Estimations will be done using gradient-based SysFit algorithm in IQRtools or SAEM algorithm in Monolix. Other appropriate methods may be used if advisable.

Inter-individual variability (IIV) is implemented for normally distributed parameters using the following equation with θ_0 as population average parameter, θ_i as individual parameter, and η_i as random effect that is distributed normally around zero ($\eta_i \sim N(0, \omega^2)$).

$$\theta_i = \theta_0 + \eta_i$$

The following equation is used for log-normally distributed parameters.

$$\ln(\theta_i) = \ln(\theta_0) + \eta_i$$

Continuous covariates on log-normally distributed parameters will be implemented as follows.

$$\theta_i = \theta_0 \cdot \frac{COV_i}{COV_{median}}^\beta \cdot \eta_i$$

θ_i represents the individual parameter, θ_0 the population mean value, COV_i the individual covariate value, COV_{median} the population median covariate value, β the covariate coefficient, and η_i the individual random effect.

Categorical covariates on log-normally distributed parameters will be implemented as follows.

$$\theta_i = \theta_0 \cdot \sum_j (e^{\beta_j \cdot COV_{ij}}) \cdot \eta_i$$

The individual covariate values COV_{ij} are 1 if participant i belongs to the j^{th} category of the covariate and 0 otherwise. $\beta_{j,i}$ is the covariate value for the j^{th} category. For one category, i.e. the reference, $\beta_{j,i}$ is 0.

For the NLME modeling with Monolix, the log-likelihood and the Fisher information matrix will be approximated by linearization. The number of iterations in the burn-in and the accumulation phase will be 500 and 200 respectively, but might be adjusted if required based on inspection of parameter estimate and objective function traces along estimation iterations. Individual parameters will be determined as conditional modes.

For PD modelling with IQRtools SysFit implementation a non-linear fixed-effects modelling approach is employed. Typical and individual parameters are both treated as fixed effects. The parameterization of individual parameters and covariates is fully consistent with the NLME parameterization above. The variances ω^2 of NLME random effects are accounted for by quadratic priors, $l_{prior}(\eta) = \frac{1\eta^2}{2\omega^2}$, added to the log-likelihood function, where the values for ω^2 are fixed and the η parameters are estimated. The profile-likelihood method [RAU09,

KAS19] is used to compute confidence intervals of the parameters estimated with the SysFit approach.

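### The covariate equations in SAP 10.6.1 contradict the log-normal definition above them: both multiply by the zero-mean random effect itself, and the categorical one adds over categories

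*SAP*

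**What the plan says.** SAP 10.6.1 introduces `η_i` as a normal random effect with mean zero and variance `ω²`. For log-normal parameters it gives "\ln(\theta_i) = \ln(\theta_0) + \eta_i".

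It then gives two covariate equations, both explicitly for log-normal parameters:

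- Continuous: "\theta_i = \theta_0 \cdot \frac{COV_i}{COV_{median}}^\beta \cdot \eta_i", with the legend "and η_i the individual random effect". The symbol is not redefined.
- Categorical: "\theta_i = \theta_0 \cdot \sum_j (e^{\beta_j \cdot COV_{ij}}) \cdot \eta_i". The indicators "are 1 if participant i belongs to the j^{th} category of the covariate and 0 otherwise", and the reference is one of the categories: "For one category, i.e. the reference, $\beta_{j,i}$ is 0".

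Later in the same section, on the SysFit fits: "The parameterization of individual parameters and covariates is fully consistent with the NLME parameterization above".

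SAP 10.6.3 assumes log-normality for every PD parameter except PLerr. SAP 10.2 lists sex and race among the covariates available. Nothing elsewhere in the SAP restates or corrects the equations, and Protocol 9.4.2 refers to the SAP for the details of the modelling.

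**The concern.** A covariate equation for a log-normal parameter should reduce to the base definition when the covariate sits at its median or the participant is in the reference category. Neither equation does. The section therefore prescribes two incompatible models for the same parameter, and the statement about SysFit carries the conflict into the second estimation method.

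At stake is the written record of the primary analysis. An independent programmer could not reproduce a covariate model from this text, and a reader could not tell what a reported `θ_0` or β means. If a covariate were selected and coded literally, the parameter would have an impossible distribution. The individual PK estimates are also regressors in the PD fit (SAP 10.6.1, step 3), so a PK covariate is not isolated from the primary endpoint.

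**Working it through.** The plan gives no figure to reproduce; the check is algebra on its own equations.

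**Inputs.** From SAP 10.6.1: `η_i ~ N(0, ω²)`; the base definition `θ_i = θ_0·exp(η_i)`; the two covariate equations; 0/1 indicators; β = 0 for the reference. From SAP 10.6.3: `ω = 0.2` in SysFit, used here for illustration. `θ_0 = 1` is an arbitrary scale.

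**Step 1: the bare random effect (both equations).** Put the covariate at its median. The continuous equation gives `θ_0·1^β·η_i = θ_0·η_i`, where the base definition gives `θ_0·exp(η_i)`. With `θ_0 = 1` and `ω = 0.2`:

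| | Base definition, `exp(η)` | As written, `η` |
|---|---|---|
| Value at η = 0 | 1 | 0 |
| P(θ_i < 0) | 0 | 0.50 |
| Central 95% range | 0.68 to 1.48 | −0.39 to 0.39 |

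The 0.50 holds for any ω, because `η_i` is symmetric around zero. Estimation does not rescue this form. `θ_0·η_i` is unchanged if `θ_0` is multiplied by a constant c and `η_i` is divided by c. So with ω estimated, only the product `θ_0·ω` could be identified. With ω fixed, the SysFit penalty `η²/(2ω²)` falls by the factor c² and would favour an ever larger `θ_0`.

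**Step 2: the sum (categorical equation only).** Each category the participant is not in contributes `e^0 = 1`. The covariate factor is therefore:

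- reference: `J` (should be 1);
- category k: `e^β_k + (J − 1)` (should be `e^β_k`).

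The ratio of category k to the reference is `(J − 1 + e^β_k)/J`. For `e^β_k = 2`:

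| J | Reference factor | Category-k factor | Ratio | Lower bound of ratio, (J−1)/J |
|---|---|---|---|---|
| 2 | 2 | 3 | 1.50 | 0.50 |
| 3 | 3 | 4 | 1.33 | 0.67 |
| 4 | 4 | 5 | 1.25 | 0.75 |

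If the sum were meant to leave out the reference, its factor would be J − 1. That is right for two categories but still wrong for three or more (2 for J = 3, 3 for J = 4).

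**Step 3: what fitting does with the sum.** Assume `exp(η_i)` is restored and the true ratio is r. The fit sets `(J − 1 + e^β_k)/J = r`, so `e^β_k = J·r − (J − 1)`, and `θ_0` becomes the reference typical value divided by J. For J = 2 and r = 1.35, `e^β = 2 × 1.35 − 1 = 1.70`, so β is about 0.53 instead of ln(1.35) = 0.30. The fitted group ratio is still 1.35; `θ_0` and β no longer mean what they are said to mean. If r is below (J−1)/J, `e^β_k` would have to be negative and the effect cannot be fitted.

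**Step 4: the usual forms.** `θ_0·(COV_i/COV_median)^β·exp(η_i)` and `θ_0·exp(Σ_j β_j·COV_ij)·exp(η_i)` give a reference factor of 1 for every J, a ratio of `e^β_k`, and no negative values. Both return the SAP's own definition at the median or reference.

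**The case against.** The strongest reply is that the intended model is plain. The log-normal definition stands directly above, the covariate equations are announced as applying to log-normal parameters, and SAP 10.6.3 repeats the assumption. A literal coding would also be unlikely to survive SAP 10.6.1.1, which asks for convergence, plausible estimates, random-effect histograms and visual predictive checks at each dose. All of this stands, and it is why a notation error is the likeliest explanation.

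Covariates are also optional (SAP 10.6.2 and 10.6.3), in a study of at most 18 participants. This stands too.

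A reader might go further and infer that a 35% effect would be reported as 17.5%, since `(1 + 1.35)/2 = 1.175`. That holds only if β were fixed at 0.3. The plan estimates `θ_0` and β, and step 3 shows that the fitted ratio stays at 1.35. A reader might also infer that E_max, EC50, MIC and the patient simulations are wrong in any case. The documents do not support that either: without covariates the base equation applies, and SAP 10.1 and 10.8 take patient PK from an existing model.

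A symbol lost in text extraction from the PDF cannot be wholly excluded; brackets around the covariate ratio appear to be missing. But `η_i` is bare in both equations, the legend calls it the random effect, the categorical equation keeps its own exponential, and a lost exponent on `η_i` would not account for the sum.

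**Conclusion.** The two equations are wrong as written and contradict the definition in their own section. Followed literally, they give a value of 0 at `η = 0`, negative values for half of individuals, and a categorical factor of J for the reference. With `exp(η_i)` restored, the sum still mislabels `θ_0` and β and rules out ratios below (J−1)/J: 0.50 for two categories, 0.67 for three.

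The practical reach is limited and conditional. It needs a covariate to enter the PK or PD model and the code to follow the text. Base-model E_max, EC50 and MIC are untouched. These equations enter the patient simulations only through a PD covariate. The conclusion assumes that the sum runs over all categories, as the text's treatment of the reference implies, and that no other document governs. Protocol section 9 mentions a separate modelling analysis plan, which is not among the two documents; if it has the right forms, the SAP should still agree with it. This should be corrected, but it does not put the trial's analysis in doubt by itself.

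**What to change.** Replace the two equations in SAP 10.6.1 with:

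- continuous: `θ_i = θ_0·(COV_i/COV_median)^β·exp(η_i)`, with the ratio in brackets;
- categorical: `θ_i = θ_0·exp(Σ_j β_j·COV_ij)·exp(η_i)`, with β = 0 for the reference and one consistent subscript on β.

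State that both reduce to the log-normal definition at the median or reference category. Have the modelling group confirm that the Monolix and SysFit code uses these forms, and record that in the technical appendix to the study report. The cost is two lines of text and a short code check. No data, sampling or design element changes.

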10.6.1.1 Model evaluation

Assessment of model adequacy and decisions about increasing model complexity will be driven by the data and guided by goodness-of-fit criteria, including

1. visual inspection of diagnostic scatter plots (observed vs. predicted concentration, residual/weighted residual vs. predicted concentration or time and histograms of individual random effects, for example),
2. successful convergence of the minimization routine with at least 2 significant digits in parameter estimates,
3. plausibility of parameter estimates,
4. precision of parameter estimates,
5. correlation between model parameter estimation errors < 0.95, and
6. the Bayesian information criterion (BIC), given the minimum objective function value and number of estimated parameters.

For the nonlinear fixed effects models, additional diagnostic plots will be produced:

7. objective function values across multiple fits from randomised initial guesses, and
8. profile likelihood plots

All parameter estimates will be reported with a measure of estimation uncertainty, such as the relative standard error of the estimates. The individual PK fits will be used to evaluate the adequacy to use the individual PK parameter estimates as regression parameters for PD modeling.

The adequacy of simulation with the selected models will be evaluated by visual predictive checks (VPCs). VPCs for each dose level will be performed by simulation of the study 200 times taking parameter estimation uncertainty into account. 95%-confidence intervals for the 5th percentile, the median, and the 95th percentile will be derived and compared to the corresponding values based on the data.

10.6.2. PK modeling

The PK of Pyronaridine will be modeled using compartmental models describing the absorption after oral administration, distribution between central and peripheral compartments, and the elimination from the central compartment. The visual data analysis will guide the selection of models that will be tested (e.g., with respect to number of compartments, linear or saturable elimination, absorption kinetics and error model). Covariates will be included if appropriate. Estimations will be done using SAEM algorithm in Monolix. Other appropriate methods may be used if advisable.

10.6.3. PD modeling

PD model development will be done using gradient based algorithms in IQRTools SysFit. The selected model will then be estimated with SAEM in Monolix to allow for estimation of IIV. Other appropriate methods may be used if advisable. As a general concept the changes in living parasite P are modeled as the effect of a net exponential growth rate GR and a killing or clearance rate $Kill$ due to Pyronaridine. The initial parasitemia P_{base} at time t_0 will be derived from the mean parasitemia which was observed at treatment administration and a parameter $PLerr$ to allow for population and individual deviations. The equations are expressed in the log-scale such as:

$$\frac{dPL}{dt} = GR - Kill$$
$$PL(t_0) = PL_{base} + PL_{err}$$

where $PL = \ln(P)$ is the log-transformed parasite counts.

Three different models describing the relationship of Pyronaridine blood concentration on the killing rate will be tested:

(1) The " E_{max} -model" assumes a direct effect of concentrations on parasite killing/clearance, such as:

$$Kill = E_{max} \cdot \frac{C_c^{Hill}}{C_c^{Hill} + EC_{50}^{Hill}}$$

where C_c is the concentration in the central compartment, E_{max} is the maximum effect of the drug, EC_{50} is the concentration that results in 50% of the maximum effect and $Hill$ is the Hill coefficient.

(2) The "Turnover model" implements an indirect response model reflecting the idea that the kinetics of drug-receptor binding lead to a lagged concentration-effect relationship, such as:

$$Kill = E_{max} \cdot R$$
$$\frac{dR}{dt} = k_{in} \left(\frac{C_c^{Hill}}{C_c^{Hill} + EC_{50}^{Hill}} - R \right)$$

where k_{in} represents the binding rate of the drug to a "receptor", which results in a lag-time in the response. Furthermore, EC_{50} represents the concentration that results in a 50% occupancy of the receptor which leads to 50% of the maximum effect given enough time to reach it.

(3) The "Clearance model" assumes that the observed parasites are a mixture of living and dead parasites. The drug has a direct effect on the killing rate of the parasites, and then the parasites are cleared, but still observed. Therefore, the equations, in the normal scale, are:

$$\frac{dP_{Alive}}{dt} = P_{Alive} \cdot (GR - Kill)$$
$$\frac{dP_{Dead}}{dt} = P_{Alive} \cdot Kill - CLpara \cdot P_{Dead}$$
$$Kill = E_{max} \cdot \frac{C_c^{Hill}}{C_c^{Hill} + EC_{50}^{Hill}}$$
$$P_{obs} = P_{Alive} + P_{Dead}$$
$$P_{Dead}(t_0) = 0$$

where $CLpara$ is the clearance rate of dead parasites, and P_{obs} is the count of measured parasite. If viable parasitemia is available then it is possible to differentiate between the killing rate and the clearance rate. Otherwise, both populations are measured indistinguishably, and E_{max} is fixed to the *in vitro* E_{max} value for this model.

During base model building, the Hill coefficient may not be identifiable. Then the best value for the Hill coefficient will be determined by estimating models with fixed Hill coefficients and selecting the best model based on the Bayesian information criterion (BIC). Considered Hill coefficients are 1, 2, 3, 5, 7, and 10. If covariate modeling is performed, the Hill coefficient is fixed in the value determined in the base model building.

IIV will be assumed on all parameters but the Hill coefficient. Parameters are assumed to be log-normally distributed besides the log-transformed deviation from the baseline parasitemia value $PLerr$ for which normal distribution will be assumed. The standard deviation of the IIV will be fixed to 0.2 for the SysFit approach. When parameters are estimated with Monolix, standard deviations of the IIV will be estimated.

Using the SysFit approach for PD modelling, parameter estimation will be started from 24 initial guesses. Identifiability of the best fit will be analysed using the profile likelihood method.

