10.7. Derivation of secondary efficacy parameters

The minimum inhibitory concentration (MIC), the minimal parasiticidal concentration (MPC90), and the PRR48 are derived from the PD models. The MIC is defined as the concentration when parasite clearance by the drug equals the parasite growth, i.e., the time at which the minimum parasite concentration is observed. It is calculated with the following equation in case of the Emax model.

$$MIC = EC_{50} \left(\frac{GR}{E_{max} + GR} \right)^{1/Hill}$$

For the other models, the calculation is only valid at steady-state. However, an apparent MIC is determined by simulations as the concentration C_c at the time when the predicted parasite counts are at the minimum.

The MPC90 is defined as the concentration at which the clearance effect is at 90% of the maximum. It is calculated as follows for the Emax model.

$$MPC_{90} = EC_{50} \cdot 9^{1/Hill}$$

For the other models, the calculation is only valid at steady-state. However, an apparent MPC90 is determined by simulations as the blood concentration C_c at the time when the predicted clearance effect is at 90% of the maximum during the drug elimination phase. The PRR48 is defined as the parasite clearance achieved within 48 hours, usually given as the reduction of values on log10 transformed scale. The maximum capacity of parasite clearance in 48 hours is determined as follows assuming that concentrations are maintained well above the MPC90 for this time span.

$$PRR_{48} = 48h \frac{E_{max} - GR}{\ln(10)}$$

The actual PRR48 for a given dose is determined as the difference of predicted parasite levels between the time when the dose is given and 48 hours later.

Key efficacy parameters will be derived using the simulations of viable parasites in case the clearance model is selected as final model.

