10.8. Post-hoc Analysis

Simulations of clinical efficacy parameters and endpoints in African children

Simulations will be performed using the already available PK model established and patients Simulations will be performed for 1, 2 and 3 daily dose regimens at the adult equivalent 720mg Pyronaridine tetraphosphate. For each dose level, 200 trials with 625 participants will be performed. Dose levels, number of trials and number of participants may be adjusted if advisable. For each trial a new set of population parameters will be sampled from the uncertainty distribution and individual parameters were sampled from the IIV. The covariates age, body weight and baseline parasitemia will be sampled from a clinical dataset of real patients.

The baseline parasitemia in patients are typical 1000 fold higher than in challenge participants and in the range of 10^4 p/uL

The following parameters will be calculated (median and 95%CI):

- Cmax: maximum Pyronaridine blood concentration
- AUC: Area under the Pyronaridine blood concentration curve

- PRR48: Parasite reduction ratio after 48h
- Parasite clearance time: time to reach the microscopic LOD (10 p/uL)
- ETF CSoff: Early treatment failure clinical symptoms off; Parasitemia on day 2 higher than on day 0, irrespective of axillary temperature, or, parasitemia on day 3, or, parasitemia on day 3 $\geq 25\%$ of count on day 0.
- ETF CSon: Early treatment failure clinical symptoms on; Parasitemia on day 2 higher than on day 0, irrespective of axillary temperature, or, parasitemia on day 3 $\geq 25\%$ of count on day 0.
- LCF28: Late clinical failure at day 28: Parasitemia above LLOQ on any day between day 4 and day 28 in patients who did not previously meet any of the criteria of ETC CSon.
- LPF28 CSoff: Late parasitological failure at day 28 clinical symptoms off: Parasitemia above LLOQ on any day between day 7 and day 28 with axillary temperature $< 37.5^{\circ}\text{C}$ in patients who did not previously meet any of the criteria of ETF CSoff.
- LPF28 CSon: Late parasitological failure at day 28 clinical symptoms on: Parasitemia above LLOQ on any day between day 7 and day 28 with axillary temperature $< 37.5^{\circ}\text{C}$ in patients who did not previously meet any of the criteria of ETF CSon or LCF28.

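### When Hill cannot be identified, SAP 10.6.3 fixes it at one grid value and treats it as known, so the uncertainty for EC50, MPC90 and the 10.8 simulations leaves Hill out

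*SAP*

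**What the plan says.** SAP 10.6.3 anticipates the problem: "During base model building, the Hill coefficient may not be identifiable". In that case "the best value for the Hill coefficient will be determined by estimating models with fixed Hill coefficients and selecting the best model" on BIC, and "Considered Hill coefficients are 1, 2, 3, 5, 7, and 10". One value is kept. Two further sentences there settle how it is handled: "IIV will be assumed on all parameters but the Hill coefficient", and "If covariate modeling is performed, the Hill coefficient is fixed in the value determined in the base model building".

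SAP 10.7 derives MPC90 from the PD model: "The MPC90 is defined as the concentration at which the clearance effect is at 90% of the maximum". For the Emax model it is EC50 × 9^(1/Hill). For the turnover and clearance models an apparent value is read from simulations. Protocol 9.4.2 names MPC90 among the key derived parameters.

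Uncertainty is promised for what is estimated. SAP 10.6.1 gives profile-likelihood intervals for parameters estimated in SysFit. SAP 10.6.1.1 and Protocol 9.4.2 give relative standard errors for parameter estimates. Neither document states how the uncertainty of MPC90 is to be computed.

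SAP 10.8 then simulates patients: "For each trial a new set of population parameters will be sampled from the uncertainty distribution". Results are reported as medians with 95% intervals.

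**The concern.** The grid is used only when the data cannot determine Hill, and from then on the analysis treats Hill as known. A fixed parameter has no standard error, no profile interval and no place in the uncertainty distribution sampled in 10.8. No step averages over the grid, repeats MPC90 at competing grid values, or carries a flat Hill profile into a derived quantity.

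The branch could well be reached. Protocol 4.3 says that parasite regrowth is needed to calculate all PK/PD parameters and that a dose as low as 180 mg may be required to see it. Cohort 1 is planned at 360 to 720 mg. The maximum is 18 participants, without a formal calculation (Protocol 9.2).

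At stake is the stated precision of EC50 and MPC90, and of those simulated patient outcomes in 10.8 that depend on the concentration–killing curve.

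**Working it through.** The plan states no MPC90 interval or coverage, so there is no figure of its own to reproduce.

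**Step 1: what BIC can do here.** BIC = −2LL + k·ln(n). Within one structural model k is the same at all six fixed Hill values, so BIC differences equal −2LL differences. Values within 3.84 of the best (the 95% point of chi-squared on 1 df) are not separated by the data at the usual level.

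**Step 2: leverage of Hill (Emax model, closed form).** From SAP 10.7, MPC90/EC50 = 9^(1/Hill). Taking MIC from its definition in words (killing equals growth), MIC = EC50 × (GR/(Emax − GR))^(1/Hill). The equation printed in 10.7 has Emax + GR instead; that is a separate matter. Then MPC90/MIC = (9(Emax − GR)/GR)^(1/Hill). With an assumed Emax/GR = 4.25 (Emax 0.20/h, GR 0.047/h), the base is 9 × 3.25 = 29.25.

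| Hill | 1 | 2 | 3 | 5 | 7 | 10 |
|---|---|---|---|---|---|---|
| MPC90/EC50 | 9.00 | 3.00 | 2.08 | 1.55 | 1.37 | 1.25 |
| EC50/MIC = 3.25^(1/Hill) | 3.25 | 1.80 | 1.48 | 1.27 | 1.18 | 1.13 |
| MPC90/MIC | 29 | 5.4 | 3.1 | 2.0 | 1.6 | 1.4 |

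One grid step moves MPC90/EC50 by a factor of 3.0 at the low end (9.00/3.00) and 1.1 at the high end (1.37/1.25). For a given MIC, EC50 and MPC90 both move with Hill.

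**Step 3: coverage under assumed inputs.** Two simulations were run, with 300 trials per scenario.

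- From the documents: the Hill grid and IIV SD 0.2 (SAP 10.6.3), M3 censoring at 10 parasites/mL (SAP 10.5.2), and a half-life of about 14 days (Protocol 2.1).
- Partly derived: GR = 0.047/h. This takes 2,800 parasites in an assumed 5 L, or 0.56/mL, growing to 5,000/mL by Day 8: ln(5,000/0.56)/192 h = 0.047.
- Assumed: true Hill, EC50, Emax, residual SD and the shape of the early PK.

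*First simulation.* Emax was 0.20/h and residual SD 0.6 (ln scale), with 18 participants at 180–720 mg in all but one scenario. Conditional coverage of MPC90 in five scenarios was 54% (Hill 3, about 2 regrowths), 42% (Hill 4), 28% (Hill 1.5), 77% (Hill 3, about 6 regrowths) and 31% (Hill 4, about 6 regrowths). On average 2 to 4 grid values lay within 3.84 of the best. Coverage for MIC was 86–94%.

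*Second simulation.* Emax was 0.15/h and residual SD 0.5 or 1.2. EC50 took two levels, true Hill ran from 1 to 10, and n was 6, 12 or 18 (n = 18 only at residual SD 0.5). Ninety-one scenarios were completed.

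| Subset | Conditional coverage of MPC90 | Median |
|---|---|---|
| All 91 scenarios | 0–97% | 80% |
| True Hill on the grid (46) | 57–97% | 91% |
| True Hill off the grid (45) | 0–89% | 43% |
| Trials with two or more grid values within 3.84 (63 scenarios with at least 50 such trials) | 0–89% | 69% |
| Trials with RSE of Hill above 50% (19 scenarios with at least 40 such trials) | 31–98% | 82% |

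Coverage was below 93% in 73 of 91 scenarios. When Hill was estimated and its uncertainty carried into MPC90 by the delta method, coverage was 89–99% across all 91. Of the 19 scenarios in the last row, 18 had n = 6 and one had n = 12.

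A case in the plan's favour: n = 18, residual SD 0.5, true Hill 3, higher EC50 level. The median SE of log MPC90 was 0.053 with Hill fixed and 0.083 with Hill estimated, a ratio of 1.6. Coverage was still 97%, because the grid search picked the true value every time.

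**The case against.** **The stronger reading.** A reader might infer that the plan's 95% interval for MPC90 covers only some definite fraction, such as the 28–77% of the first simulation. The documents do not support this. They give no true Hill, EC50, Emax or residual error, and they specify no MPC90 interval at all. Only 23 of the 91 scenarios in the second simulation fell in that range. A reader might also call Hill the largest source of uncertainty in MPC90; that is not shown in general, as the n = 18 case illustrates.

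**Safeguards in the SAP.** SAP 10.6.3 plans a profile-likelihood check of identifiability. SAP 10.6.1.1 plans profile plots and predictive checks that include parameter uncertainty. SAP 10.9 promises a discussion of model limitations, and other methods are allowed if advisable. These would show that Hill is poorly identified, but none of them puts that into the uncertainty of MPC90 or into 10.8. Protocol section 9 also mentions a Modelling Analysis Plan that is not among the documents, although Protocol 9.4.2 assigns the full modelling details to the SAP.

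**Limited consequence.** There is no hypothesis test, no decision rule names MPC90, and section 10.8 is headed as post hoc and does not list MPC90 as an output. Cmax and AUC there do not depend on Hill. The effect on the other 10.8 outputs was not simulated.

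**Scope.** The multipliers apply directly only to the Emax model, one of three candidates. If Hill is estimated, its uncertainty can enter 10.8 in the ordinary way and this point falls away.

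All of this limits the size and reach of the point. It does not answer the mechanism: a value chosen because the data could not identify it is carried forward without error.

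**Conclusion.** The point holds in a conditional form. If the fixed-Hill branch is used, the plan followed as written gives uncertainty for EC50 and MPC90, and 95% intervals in 10.8, that are conditional on one selected Hill value. The Emax-model leverage is exact algebra: MPC90/EC50 spans 9.0 to 1.25 over the grid. The resulting loss of coverage depends on unknown inputs. Under those assumed it ran from 0% to nominal (97%), and it stayed at 89% or below wherever two or more grid values fitted about equally well. MIC is little affected.

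Confidence is high in the mechanism and low in any single coverage figure. This is a should-fix, conditional on the branch being used.

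**What to change.** Add to SAP 10.6.3 and 10.7, for the case where Hill is fixed:

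- Use the selected Hill for point estimates only.
- Carry Hill uncertainty into EC50, MIC and MPC90. One way is to profile Hill on a finer grid (for example 1 to 10 in steps of 0.5) and report the union of intervals over all values within 3.84 in −2LL of the best. The other is to average over the grid with BIC weights.
- At minimum, report MPC90 at every Hill value within 3.84 in −2LL of the best.
- For the turnover and clearance models, do the same with the simulated apparent MPC90.

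In 10.8, draw Hill from the same profile or BIC weights instead of holding it fixed.

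The finer-grid interval has not been tested. On the SAP's own six points, the union interval covered 80–96% in five of six scenarios but 52% where the true Hill of 1.5 fell between grid points, which is the reason for refining the grid. A short simulation before the wording is settled would be sensible.

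The cost is SAP wording, a few extra fits (a 0.5-step grid has 19 values, 13 more than now, for each structural model profiled) and a wider MPC90 interval. No trial procedure changes.
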